1.6 Study design

This is a phase 3, double-blind, randomised, placebo-controlled, study, to assess the efficacy and safety of AZD9291 versus placebo in patients with stage IB-IIIA non squamous, non small cell lung cancer (NSCLC) with a centrally confirmed, common sensitising EGFR mutations (Ex19del and L858R either alone or in combination with other EGFR mutations) as confirmed by a central test, who have had complete tumour resection, with or without postoperative adjuvant chemotherapy.

Patients will be randomised 1:1 to receive either AZD9291 or placebo. Patients must have sufficiently recovered from surgery and completed any standard of care adjuvant chemotherapy if applicable prior to randomisation. Patients must be randomised within 10 weeks of complete surgical resection if adjuvant chemotherapy was not administered and within 26 weeks if adjuvant chemotherapy was administered.

Accounting for patients who are found to have wild type EGFR, sample attrition and 10% screen fail rate for other reasons, it is estimated that 3200 patients will be screened to randomise approximately 700 patients. It is assumed that approximately 60% of patients will be recruited from Asia and 40% from non-Asian countries. The proportion of patients randomised with stage IB cancer will be 30% and the proportion of patients randomised with Stage II-IIIA cancer will be 70%. Patients will be stratified by stage (IB vs II vs III), mutation

type status as confirmed by a central laboratory using a tissue based test (Ex19Del/L858R either alone or in combination with other EGFR mutations as confirmed by a central test), and race (Asian/ non-Asian).

Following complete resection and prior to treatment initiation, all patients will be required to have a baseline CT scan (chest and abdomen including liver and adrenal glands) within 28 days of treatment initiation to confirm that disease is not present. Patients will continue on randomised treatment until recurrence of disease, treatment discontinuation criterion is met or treatment is completed. The treatment duration period is 3 years (156 weeks). Patients being on study drug at the time of DFS analysis may continue treatment until discontinuation criterion is met or 3 years (156 weeks) treatment is completed.

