- k) In the rare case where a patient is intolerant of the contrast medium, the preferred imaging would be CT chest without contrast and MRI abdomen with contrast however non contrast abdominal CT will also be accepted. All recurrences on study need to be confirmed with imaging of the chest and abdomen (including liver and adrenal glands). The imaging method used at baseline (CT or MRI) must be used at each subsequent follow-up assessment. MRI/contrast CT scans of the brain must be conducted at recurrence.
- l) Baseline scans within 28 days of first dose
- m) Required only if suspicious signs/symptoms are not covered by CT of chest and abdomen (including liver and adrenal glands) at baseline and follow-up
- n) If for any reason a sample is not drawn prior to dosing, it may be taken at any visit until the last study visit
- o) Plasma samples 10ml prior to first randomised dose on Day 1; 20-30 ml at every 12 weeks visits. If patient discontinues study treatment prior to disease recurrence, samples should continue to be collected in accordance with the scan schedule until disease recurrence is noted.
- p) Blood sampling at 4 weeks, 24 weeks, 48 weeks, 96 weeks after randomisation. Blood draw to occur 3 times at each visit at following time points: pre-dose, between 0,5 -1,5h post dose, between 2-4 h post dose. 96 week PK sample post IDMC7 analysis will not be collected.
- q) SF 36 at 12 weeks, 24 weeks and then every 24 weeks relative to randomisation (\pm 7 days) until disease recurrence
- r) Patients will be asked about any health resource use between visits (i.e., excluding routine follow-up clinic visits associated with the clinical trial but including both planned and unplanned admissions) at every scheduled visit during the study.
- s) AEs ongoing at treatment discontinuation to be followed through to resolution; thereafter, only SAEs /concomitant medications for SAEs considered related to IP and study procedures to be recorded in eCRF
- t) Investigator assessment of response/progression to be collected
- u) To establish survival status patient will be contacted in the week following date of DCO for IDMC and in the two weeks following date of DCO for primary analysis and subsequent analyses.

Table 2 Study Plan for OS period - post final DFS analysis and up to final OS analysis

	Treatment Period	Post-Treatment			Protocol Section
		Treatment discontinuation ^a	28 day Follow up ^b	Follow up for survival	
Visit	On treatment				

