4.1 Enrolment/screening period

It is recommended that the screening assessments are performed in a stepwise process beginning with the confirmation of EGFR mutation status determined by the designated central laboratory. However, screening assessments may be done in parallel to the EGFR mutation assessment, as appropriate. Procedures will be performed according to the Study Plan (Table 1). Radiological assessments and other clinical data obtained as SoC prior to consent may be used for the study, provided the assessments fall within the protocol specified period prior to the first dose of the study drug.

At screening, consenting subjects are assessed to ensure that they meet eligibility criteria. Subjects who are EGFR mutation negative or do not meet eligibility criteria must not be randomised into the study. Demographic data and other characteristics will be recorded and will include date of birth or age, gender, smoking history, race and/or ethnicity according to local regulations.

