* Results from such exploratory analyses may be reported separately from the CSR.

Exploratory Objective*:	Outcome Measure:
To collect and store biopsy material (multiple cores where possible) from all screened patients for exploratory analysis of molecular mechanisms associated with development of non-small cell lung cancer (NSCLC) and response to treatment.	Key genetic and proteomic markers to include, but not limited to, EGFR mutations, human epidermal growth factor receptor 2 (HER2), and proto-oncogene encoding Hepatocyte Growth Factor Receptor (cMET) expression and/or amplification. Data generated may be reported separately and may also form part of a pooled analysis with other AZD9291 studies.
To collect and store deoxyribonucleic acid (DNA) for future exploratory research into genes/genetic variation that may influence response to AZD9291 (safety and efficacy) and/or susceptibility to/development of cancers.	Correlation of polymorphisms with variation in pharmacodynamics, safety or response observed in patients treated with AZD9291 or comparator.
To compare the baseline tumour EGFR mutation status in all randomised patients with evaluable results from baseline plasma.	Comparison of EGFR mutation status between tumour deoxyribonucleic acid (DNA) and plasma derived ctDNA.
To compare plasma-derived ctDNA EGFR mutation status at baseline and at disease recurrence.	Comparison of EGFR mutation status in plasma samples at baseline and at disease recurrence.
To assess any changes in EGFR mutation status (including T790M) using the mandated serial plasma samples coupled with a high sensitivity method yet to be determined (retrospective).	Assessment of EGFR mutation status in serial plasma samples.
To explore the relationship between PK and selected endpoints (which may include efficacy, safety, and/or patient reported outcomes [PROs]), where deemed appropriate.	Correlation of PK with other primary/secondary/exploratory endpoints in patients treated with AZD9291.

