Analysis of EGFR Mutation Status Between Tumour DNA And Plasma-Derived CtDNA

Cross-tabulation summaries of the mutation status from EGFR mutation status from tumour DNA (Positive, Negative, Total) versus the mutation status from plasma-derived ctDNA (Positive, Negative, Unknown, Total) will be produced for:

- all screened patients who are evaluable (Positive, Negative) for baseline tumour mutation status
- all screened patients who are evaluable for both the baseline tumour mutation status and the recurrence mutation status

The concordance (i.e. both positive or both negative), sensitivity, specificity, positive predictive value (PPV) and negative predictive value (NPV) rates for the EGFR mutation status will be produced for subgroups of patients as mentioned above. The 95% CIs using Wilson score intervals will be presented for each of these, however if the number of patients in the subgroup is <30, then the Clopper-Pearson method (Clopper & Pearson, 1934) will be used to derive the 95% CI.

Sensitivity is defined as:

$$100 \times \frac{\text{number of patients who are EGFR positive from both tumour sample and plasma-derived}}{\text{number of patients who are EGFR positive from tumour sample}}$$

Specificity is defined as:

$$100 \times \frac{\text{number of patients who are EGFR negative from both tumour sample and plasma-derived}}{\text{number of patients who are EGFR negative from tumour sample}}$$

PPV is defined as:

$$100 \times \frac{\text{number of patients who are EGFR positive from both tumour sample and plasma-derived}}{\text{number of patients who are EGFR positive from plasma-derived}}$$

NPV is defined as:

$$100 \times \frac{\text{number of patients who are EGFR negative from both tumour sample and plasma-derived}}{\text{number of patients who are EGFR negative from plasma-derived}}$$

Analysis of Plasma-Derived ctDNA EGFR Mutation Status at Baseline Compared to Status at Disease Recurrence

Cross-tabulation summaries of the mutation status from the first plasma sample at baseline (Positive, Negative, Unknown, Total) versus the mutation status from the plasma sample taken at disease recurrence (Positive, Negative, Unknown, Total) will be presented:

- in patients from the FAS population who are evaluable for both the first plasma sample and the recurrence plasma sample

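### Exploratory plasma ctDNA sensitivity: as written, Unknown plasma results stay in the denominator, the second analysis population requires a recurrence result, and neither population is the one named in the objective

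*SAP*

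**What the plan says.** The exploratory objective in SAP 1.1, repeated in Protocol 2.4, is "To compare the baseline tumour EGFR mutation status in all randomised patients with evaluable results from baseline plasma".

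SAP 4.3.7.3 carries this out in two populations:
- The first is "all screened patients who are evaluable (Positive, Negative) for baseline tumour mutation status". Entry depends on the tumour test only.
- The second, which adds a condition tied to relapse, is "all screened patients who are evaluable for both the baseline tumour mutation status and the recurrence mutation status".

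Tumour status is cross-tabulated against "the mutation status from plasma-derived ctDNA (Positive, Negative, Unknown, Total) will be produced for" these two groups. Sensitivity is the number positive on both tests divided by the "number of patients who are EGFR positive from tumour sample". Wilson intervals are specified, with Clopper-Pearson for groups under 30.

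Two design facts determine who can have a baseline plasma result. The first sample is scheduled on Day 1: "Plasma samples 10ml prior to first randomised dose on Day 1" (footnote to Protocol Table 1). Protocol 4.1 adds: "Subjects who are EGFR mutation negative or do not meet eligibility criteria must not be randomised into the study".

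SAP section 6, which lists departures from the protocol, does not mention a change of population for this analysis.

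**The concern.** The sensitivity denominator depends on the tumour result alone. In the first population a tumour-positive patient with no plasma result therefore counts against the plasma test. That includes tumour-positive patients who failed screening for another reason, who have no scheduled plasma sample.

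The second population conditions a baseline accuracy measure on something that can exist only after relapse.

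Because tumour-negative patients are not randomised, sensitivity is the one accuracy measure this design can estimate. Protocol 2.4 says the tissue and plasma samples may support diagnostic development, so the reported rate should be the one the objective describes.

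**Working it through.** The documents state no sensitivity, plasma-evaluable rate or sample size for this analysis, so there is no figure to reproduce. The check is on the definitions.

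**Inputs from the documents**
- Randomised: 682 (Protocol 1.4).
- DFS events in the overall population: 196 at IDMC7, 317 planned (SAP section 7, Table 7).
- Screening plan: "sample attrition and 10% screen fail rate for other reasons, it is estimated that 3200 patients will be screened to randomise approximately 700 patients" (Protocol 1.6).

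**Assumptions, not in the documents**
- S, sensitivity among patients with an evaluable plasma result: 40% for illustration, 20% to 60% as a range.
- u, share of randomised patients with Unknown baseline plasma: 2% to 30%.

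**Step 1: first population, randomised patients only.** The rate as written is S x (1 - u). With N = 682, S = 40% and Wilson 95% intervals:

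| u | Evaluable patients only | Denominator as written |
|---|---|---|
| 2% | 267/668 = 40.0% (36.3 to 43.7) | 267/682 = 39.1% (35.6 to 42.9) |
| 10% | 246/614 = 40.1% (36.3 to 44.0) | 246/682 = 36.1% (32.6 to 39.7) |
| 20% | 218/546 = 39.9% (35.9 to 44.1) | 218/682 = 32.0% (28.6 to 35.6) |
| 30% | 191/477 = 40.0% (35.7 to 44.5) | 191/682 = 28.0% (24.8 to 31.5) |

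The absolute loss is S x u. At u = 2% it runs from 0.4 points (S = 20%) to 1.2 points (S = 60%).

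**Step 2: add tumour-positive patients who were screened but not randomised.** Suppose the planned 10% screen failure applies in full to tumour-positive patients (assumption). Then 700/0.9 = about 778 are tumour-positive, and about 78 of them have no scheduled plasma. The rate as written becomes S x 0.9 x (1 - u). It cannot exceed 90% with complete plasma in randomised patients, or 81% at u = 10%. For S = 40% and u = 10% it is 0.40 x 0.9 x 0.9 = 32.4%.

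**Step 3: second population.** A recurrence result requires a recurrence. The upper limit is 196/682 = 28.7% of randomised patients at IDMC7, in line with the 29% maturity in SAP Table 7, and 317/682 = 46.5% at the planned event count. Both are ceilings, because DFS events include deaths without recurrence.

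If baseline plasma-positive patients recur R times as often as plasma-negative patients (assumption), the rate in this subset is S x R / (S x R + 1 - S). For S = 40%:
- R = 1: 40%
- R = 1.5: 0.60/(0.60 + 0.60) = 50%
- R = 3: 1.20/(1.20 + 0.60) = 67%

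An evaluable baseline plasma result is not required here either, so Unknowns could pull the rate back down.

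**Step 4: the other measures in randomised patients with evaluable baseline plasma.** Apart from enrolment errors, all of them are tumour-positive.
- Specificity is 0/0.
- NPV has a numerator of zero whatever the test does.
- PPV is 100% by construction.
- Concordance reduces to sensitivity.

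**The case against.** The SAP nowhere says that Unknown is scored as negative. SAP 3.1.3 says missing data are treated as missing, and a programmer might drop Unknowns on that basis. The Unknown column proves little by itself: the next analysis in 4.3.7.3 is limited to patients evaluable on both plasma samples, yet its table has the same column. This stands as a caution, and a reader should not infer an explicit instruction to count untested patients as negative. It does not rescue the formula. The written denominator is set by tumour status alone, the population requires no plasma result, and the missing-data rule gives no denominator. Unknowns stay in by the definition itself.

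The recurrence wording may well be a slip. Tumour plus baseline plasma is the pairing that fits the analysis title, and the recurrence phrase resembles the analysis that follows. It is also unclear whether the phrase means plasma or tumour. A reader might infer that this population would overstate sensitivity. The documents contain nothing on ctDNA detection by later relapse, so an upward bias is plausible but undocumented. If the phrase is a slip, correcting it is the change needed.

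A reader might also take the 78 or so unsampled tumour-positive patients as a protocol figure. It is not. The 10% is a planning estimate that is not tied to tumour-positive patients, and Protocol 4.1 allows screening assessments to run in parallel with EGFR testing.

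Finally, the objective asks for a comparison of mutation status and does not name sensitivity, and the cross-table shows Unknown separately, so the first population's rate can be recomputed by hand. Both points are right. They limit the harm but do not make the stated rate correct.

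**Conclusion.** The rule is wrong as written, within an exploratory analysis that has no bearing on DFS, OS or the multiplicity scheme. Taken literally, sensitivity in the first population is reduced by the factor (1 - share Unknown), where Unknown includes tumour-positive patients who were never randomised. The second population limits a baseline comparison to patients who recurred and could bias it, in a direction the documents do not establish. Neither population matches the objective, and the SAP does not list the difference as a change from protocol.

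The size rests on an Unknown share that the documents do not give. Plasma is scheduled on Day 1 for every randomised patient, so the share may be small and the loss then negligible; it becomes material only toward the upper end of the assumed range. The screen-failure component, the detection rates and the recurrence ratio are likewise assumptions. No passage ties a decision to this rate.

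**What to change.** In SAP 4.3.7.3:
- In the second population, replace the recurrence status with the baseline plasma mutation status, and limit the population to randomised patients with a Positive or Negative baseline plasma result.
- Compute sensitivity and concordance in that population.
- Report the number with Unknown plasma separately, with reasons (no sample, failed test). If a rate with Unknown counted as not detected is wanted, give it as a labelled secondary figure.
- State that specificity and NPV cannot be estimated in this population and that PPV is uninformative, because tumour-negative patients are not randomised.

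The cost is a few lines of SAP text and no new data. The drawback is that patients without a plasma result leave the denominator, so their number must be shown beside the rate. The change does not make specificity or NPV estimable, since the design schedules no plasma sample for tumour-negative patients.

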4.3.4 Survival follow-up (up to final OS analysis)

Assessments for survival should be made every 24 weeks up to 5 years (264 weeks) after randomisation and yearly thereafter following disease recurrence. Survival information may be obtained via telephone contact with the patient, patient's family or by contact with the patient's current physician.

In addition to the survival status, the following assessments are required post recurrence as detailed in the study plan ([Table 2](#)).

- Anti-cancer therapy, radiotherapy and surgery
- Serious Adverse event collection (causally related)
- Subsequent response and progression data (PFS) in accordance with local practice until the first confirmed disease progression on a subsequent treatment (not collected post primary analysis or post 'Final DFS analysis' if required)

Survival data will be collected up to the time of the final OS analysis. Patients should be contacted in the week following date of DCO for IDMC and in the two weeks following date of DCO for primary analysis and subsequent analyses. The status of ongoing, withdrawn (from the study), and "lost to follow-up" patients at the time of each of the efficacy analyses should be obtained by the site personnel by checking the patients notes, hospital records, contacting the patient's general practitioner, and checking publicly available death registries. In the event that the patient has withdrawn consent to the processing of their personal data, the survival status of the patient can be obtained by site personnel from publicly available resources where it is possible to do so under applicable local laws.

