5.1 Efficacy assessments

5.1.1 Disease-free survival

Disease-free survival is the primary endpoint in this study and is defined as the time from the date of randomisation until the date of disease recurrence or death from any cause in the absence of disease recurrence. Disease recurrence is defined as evidence of disease recurrence on CT or MRI scan and/or pathological disease on biopsy by investigational site assessment.

The imaging modalities used for radiological assessments will be CT scans of the chest and abdomen (including liver and adrenal glands) with contrast. In the rare case where a patient is intolerant of the contrast medium the preferred imaging would be CT chest without contrast and MRI abdomen with contrast; however a non-contrast abdominal CT will also be accepted. The methods used at baseline (CT or MRI) must be used at each subsequent follow-up assessments. A pre-surgical MRI or contrast CT scan of the brain is considered standard of

care and must be done prior to surgery. Patients in whom this was not done prior to surgery may still be enrolled providing that appropriate imaging is performed prior to randomisation. Any other sites where disease is suspected at baseline must also be imaged to confirm absence of disease prior to randomisation into the study. The baseline assessments should be performed within 28 days prior to study drug initiation. Subsequent assessments are to be performed at 12 week, 24 week and then every 24 weeks until 5 years (264 weeks), and then yearly thereafter relative randomisation, until disease recurrence is recorded. If a patient discontinues treatment prior to disease recurrence or receives other anti-cancer treatment, patient should continue to be imaged in accordance with this schedule until disease recurrence is noted. It is important to follow the assessment schedule as closely as possible. If scans are performed outside of the scheduled visit (\pm 7 days window interval) and the patient has not recurred, every attempt should be made to perform the subsequent scans at their scheduled time points. Any other sites at which a new disease is suspected should also be appropriately imaged during the study.

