5.1.2.3 Post-recurrence

Following recurrence patient management is at the discretion of the investigator, and tumour assessments will be in accordance with local policy. Date of the first subsequent progression as determined by the investigator will be recorded.

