3.2. Efficacy Assessments

3.2.1. Disease Free Survival

DFS is defined as the time (in days) from the date of randomisation until the date of disease recurrence or death (by any cause in the absence of recurrence) regardless of whether the patient withdraws from randomised therapy or receives another anti-cancer therapy prior to recurrence (i.e. date of DFS event or censoring – date of randomisation + 1).

Patients who are disease-free and alive at the time of analysis will be censored at the date of their last assessment for disease recurrence. However, if the patient recurs or dies immediately after two or more consecutive missed visits, the patient will be censored at the time of the latest evaluable assessment for disease recurrence prior to the two missed visits. Given the scheduled visit assessment scheme (i.e. twelve-weekly for the first 24 weeks and then twenty-four-weekly thereafter) the definition of 2 missed visits will change. If the previous assessment is less than study day 78 (i.e. week 11) then two missing visits will equate to 25 weeks since the previous assessment, allowing for late visit (i.e. 2×12 weeks + 1 week for a late assessment = 25 weeks). If the two missed visits occur over the period when the scheduled frequency of assessments changes from twelve-weekly to twenty-four-weekly this will equate to 38 weeks (i.e. take the average 12 and 24 weeks which gives 18 weeks and then 2×18 weeks + 1 week of an early assessment + 1 week for a late assessment = 38 weeks). The time period for the previous assessment will be from study days 78 to 161 (i.e. week 11 up to week 23). If the previous assessment is from week 23 (day 162) onwards (when the scheduling

changes to twenty-four weekly assessments), two missing visits will equate to 50 weeks (i.e. 2 x 24 weeks + 1 week for an early assessment + 1 week for a late assessment = 50 weeks).

If the patient has no evaluable visits or does not have baseline data (chest, abdomen & brain scans), they will be censored at Day 1 unless they die within two visits of baseline (24 weeks plus 1 week allowing for a late assessment within the visit window) in which case the event will be used.

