The concordance rate and its 95% CI for the EGFR mutation status of the first plasma sample versus the progression plasma sample will also be presented for groups described above.

Analysis of Time to New Brain Lesion or Death

Time to new brain lesion or death will be summarised for the stage II/IIIA and overall population using the same methodology and model as for the analysis of DFS with the exception that the sensitivity, subgroup and exploratory analyses will not be performed. An event is a recurrence with evidence of a CNS lesion or death by any cause. Patients without an event will be censored at the last evaluable disease assessment. The HR for the treatment effect together with its 95% CI will be presented. No multiplicity adjustment will be applied as this is viewed as a supportive endpoint.

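### Time to new brain lesion or death: after a first recurrence outside the CNS only patients who die stay at risk, which tilts the hazard ratio towards osimertinib

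*SAP*

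**What the plan says.** SAP 4.3.7.3 sets two rules for this endpoint. On events: "An event is a recurrence with evidence of a CNS lesion or death by any cause". On censoring: "Patients without an event will be censored at the last evaluable disease assessment". The analysis is run in the stage II/IIIA and overall populations "using the same methodology and model as for the analysis of DFS with the exception" that the sensitivity, subgroup and exploratory analyses are dropped. An HR with 95% CI is to be presented, without multiplicity adjustment, as supportive. The section does not say what happens to a patient whose first recurrence is outside the CNS.

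The Protocol fixes what is observed after that point. Section 5.1.1 schedules scans at 12 and 24 weeks, every 24 weeks to 5 years, "then yearly thereafter relative randomisation, until disease recurrence is recorded". Section 5.1.2.3 adds: "Following recurrence patient management is at the discretion of the investigator, and tumour assessments will be in accordance with local policy". Deaths are still collected under section 4.3.4: "Assessments for survival should be made every 24 weeks up to 5 years (264 weeks) after randomisation and yearly thereafter following disease recurrence".

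SAP 3.2.1 has a further rule for DFS: "if the patient recurs or dies immediately after two or more consecutive missed visits, the patient will be censored" at the last evaluable assessment before the gap. SAP 4.3.7.3 does not say whether this carries over.

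**The concern.** DFS does not have this problem, because any recurrence is itself the event and ends follow-up. Once the event is narrowed to CNS recurrence or death, a first recurrence elsewhere ends scheduled imaging but is not an event. Two patients with the same recurrence on the same day are then treated differently according to what happens later: one who dies stays at risk until death and counts as an event, while one who survives leaves the risk set at about the recurrence scan. Time after recurrence is counted only for those who die, so censoring depends on the outcome.

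This does not cancel between arms. Protocol 1.4 reports an overall DFS HR of 0.20, so placebo has many more patients in this position. CNS protection is part of the trial's rationale (Protocol 1 and 1.2), so readers will look at this HR, and the sensitivity analyses that might expose the problem are switched off.

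**Working it through.** The documents give no figure for this endpoint, so there is none to reproduce. The check is a simulation of randomisation, first recurrence (CNS or non-CNS, detected at the protocol scan times) and death.

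**Inputs from the documents**
- 343 placebo and 339 osimertinib patients; DFS HR 0.20 overall; 29 deaths, 20 placebo and 9 osimertinib (Protocol 1.4).
- 196 DFS events overall at IDMC7 (SAP 7).
- Recruitment from 26 August 2015 (Protocol Appendix A) to the cut-off of 17 January 2020 (Protocol 1.4): at most about 53 months of follow-up.

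**Assumptions not in the documents**
- Exponential hazards. Follow-up 9 to 52 months (IDMC7-like) or 44 to 87 months (later).
- CNS share of placebo recurrences 15% or 37%. The upper value borrows the 37.1% that Protocol 1 cites for an earlier adjuvant erlotinib trial.
- Monthly death hazard 0.0006 before and 0.0065 after recurrence. For the case with no effect on CNS recurrence or death: 0.0014 in both states.

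**Calibration.** With a CNS HR of 0.2 and IDMC7-like follow-up, the runs give 153 + 44 = 197 DFS events (15% share) or 154 + 44 = 198 (37%), against 196 reported, and 21 + 10 = 31 deaths against 29. With no CNS effect, DFS events rise to 153 + 64 = 217 or 153 + 91 = 244. Those cases are hypothetical and do not fit the reported data.

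**Where the extra events come from** (IDMC7-like, 15% share, no CNS effect, rounded means per trial)

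| | Placebo | Osimertinib |
|---|---|---|
| DFS events | 153 | 64 |
| CNS at first recurrence | 23 | 28 |
| CNS at first recurrence, or death without recurrence | 28 | 33 |
| Non-CNS first recurrences | 153 − 28 = 125 | 64 − 33 = 31 |
| Deaths after these | 14 | 3 |
| Events under the SAP rule | 28 + 14 = 42 | 33 + 3 = 36 |

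The rule adds 14/28 = 50% to the placebo events and 3/33 = 9% to the osimertinib events. The other 125 − 14 = 111 placebo and 31 − 3 = 28 osimertinib patients leave the risk set at the recurrence scan.

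**Hazard ratios** (Cox model, Breslow ties, 300,000 patients per arm). In the last column a non-CNS recurrence ends follow-up for everyone. In the column before it, everyone is followed throughout for a CNS lesion at any time or death.

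| True CNS HR, follow-up, CNS share | SAP rule | SAP rule + two missed visits | Full follow-up | First event |
|---|---|---|---|---|
| 1, IDMC7-like, 15% | 0.72 | 0.82 | 0.78 | 1.00 |
| 1, IDMC7-like, 37% | 0.89 | 0.93 | 0.90 | 0.99 |
| 1, later, 15% | 0.59 | 0.80 | 0.71 | 0.99 |
| 1, later, 37% | 0.82 | 0.93 | 0.86 | 1.00 |
| 0.5, IDMC7-like, 15% | 0.45 | 0.50 | 0.50 | 0.58 |
| 0.5, IDMC7-like, 37% | 0.49 | 0.51 | 0.51 | 0.54 |
| 0.2, IDMC7-like, 15% | 0.28 | 0.31 | 0.33 | 0.34 |
| 0.2, IDMC7-like, 37% | 0.25 | 0.26 | 0.28 | 0.27 |

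**No effect on CNS recurrence or death** (treatment acts on non-CNS recurrence only). This isolates the censoring. The SAP rule gives about 0.92 to 0.96 at IDMC7-like follow-up and 0.84 to 0.93 later. Consistent handling gives 0.99 to 1.01. With the two-missed-visits rule the HR is about 0.95 to 0.96. The chance of a nominally significant benefit is 4 to 15% instead of 2.5%.

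**The case against.** **A stronger reading.** A reader might infer that the rule manufactures a CNS benefit, taking the whole gap between 0.7 to 0.9 and 1.00 as bias. The documents do not support that. The endpoint openly includes death, and a drug that prevents recurrences leading to death has a real effect on it. In the table full follow-up already gives 0.78 and 0.90 at IDMC7-like follow-up, so censoring alone accounts for 0.78 − 0.72 = 0.06 and 0.90 − 0.89 = 0.01. Later it accounts for 0.71 − 0.59 = 0.12 and 0.86 − 0.82 = 0.04. The first-event HR of 1.00 answers a narrower question. Hazards that give much larger distortions imply about twice the 29 deaths reported.

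**Censoring at the recurrence scan is inferred.** Subsequent progression data are collected after recurrence (Protocol 4.3.4), and SAP 3.2.4 uses progression assessment dates for PFS. If such local assessments count as evaluable here, survivors are censored later and the bias is smaller. The SAP does not say. This point stands as an ambiguity that itself needs closing.

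**The DFS missed-visits rule may apply.** If so, the bias shrinks but remains, as the table shows.

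**The direction is not universal.** If CNS risk rises fourfold after a non-CNS recurrence, the SAP-rule HR (0.72) is weaker than the HR for a CNS lesion at any time or death (0.63), because later CNS lesions are missed.

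**The endpoint is exploratory,** outside the testing hierarchy, and SAP 4.3.6 summarises brain metastases by arm separately. That limits the consequence. It does not justify treating survivors and non-survivors differently after the same recurrence.

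**Conclusion.** The point holds as an inconsistency in a stated rule. Relative to a version that handles non-CNS recurrence alike for all patients, SAP 4.3.7.3 biases the HR towards osimertinib. From censoring alone, with no effect on CNS recurrence or death, the HR is about 0.92 to 0.96 at IDMC7-like follow-up and 0.84 to 0.93 later. With no CNS effect but higher mortality after recurrence it is about 0.7 to 0.9 at IDMC7-like follow-up, against 1.00 for first-event handling; part of that difference is a genuine mortality effect on the composite. If the true CNS HR is about 0.2, in line with the reported DFS HR, the move is only from 0.27 to 0.34 down to 0.25 to 0.28.

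The sizes rest on the assumed hazards, follow-up and CNS share, and on censoring close to the recurrence scan. The distortion grows with follow-up and is limited at IDMC7 by the 29 deaths. The confirmatory tests are untouched. It would be wrong to conclude that any observed CNS benefit is an artefact.

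**What to change.** Amend SAP 4.3.7.3 so that a first non-CNS recurrence is handled the same way whether or not the patient later dies:
- Count as the event a CNS lesion at first recurrence, or death without prior recurrence.
- For the cause-specific HR, censor every patient at first non-CNS recurrence.
- Show Aalen-Johansen cumulative incidence by arm, with non-CNS recurrence as a competing event.
- State that deaths after non-CNS recurrence are not counted here and are captured in OS.
- Say which assessments count as evaluable and whether the two-missed-visits rule applies.

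The cost is one paragraph and one re-run on data already collected. The downside is fewer events (28 against 42 on placebo in the worked case) and a narrower, first-event estimand. Keeping the wider composite instead would require survivors to stay at risk after recurrence, when the Protocol schedules no further CNS imaging.
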